Using Stata's 'power logrank' command with Schoenfeld's formula, 171 participants per arm would be required for 90% power to detect a hazard ration of 0.6. However, the design of this study, with therapy offered in the intervention arm only, results in a partially nested data structure. We anticipate little therapist effect, but to allow for variation we recalculated the sample size using 'clsampsi' in Stata with an ICC of 0.01 in the intervention arm. With an average cluster size of 11, 198 participants would be required in each arm for 90% power to detect a difference in relapse of 40% in the control arm and 24% in the intervention arm. Inflating for the expected 2% drop out, we require a total sample size of 404. Based on this sample size, we will need to recruit 17 participants per month across all NHS Trusts (see

.

[figure not shown]

Figure 1. CONSORT diagram of the CaFI RCT procedures.

Participants and recruitment procedures

As recruitment will be within communities previously labelled 'hard-to-reach', we shall adopt engagement and recruitment strategies informed by our PPI work and previous HS&DR (CaFI) study. These may include but are not limited to using local media, working with Faith-Based Organisations (FBOs), voluntary sector agencies and community groups.

Within services, we shall place advertisement posters and flyers in participating sites accessible to service users, carers and advocates. We anticipate that the study will be adopted onto the NIHR portfolio. Accordingly, NIHR Clinical Research Network (CRN) Clinical Studies Officers (CSOs) will support recruitment, helping to identify and recruit suitable participants. CSOs and RAs will work collaboratively to publicise the study and inform clinical staff about the inclusion criteria. Recruitment packs, including the study Participant Information Sheet (PIS), will be provided for service users who are deemed well enough to participate by their clinical teams, who have the capacity to consent and who gave permission to be contacted by the research team. Service users who remain interested will be invited to meet with the RA to receive further information about the study and ask any questions before being consented into the study. Consenting participants will be asked to complete baseline assessments during the initial meeting. An additional meeting will be arranged if this is not feasible.

Target population

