- Former service users as 'befrienders' or 'peer support workers' whom we shall recruit, deploying them where service users without families are unable to nominate anyone.

Design rationale - Randomised Controlled Trial

The RCT is a multi-site study across the UK, in four geographical locations (North West, Midlands, London and South England) in seven NHS Mental Health Trusts, plus two contingency Trusts taking place in psychiatric hospitals, community and forensic settings. Our target population is Sub Saharan African and Caribbean people diagnosed with psychoses and their families (including those who self-

identify as 'Black British' and 'Mixed' heritage). We will recruit 404 family units (all sites combined) which equates to 202 family units in each arm.

The trial will involve testing the Culturally adapted Family Intervention (CaFI) with service users and their families over 10 one-hour sessions within a 20 week 'therapy window' by therapists trained in CaFI therapy delivery. CaFI comprises of five components each delivered over two sessions. The sessions will be delivered by a Lead Therapist (Band 7) and a Co-Therapist (Band 4). The control group will receive usual care.

Our primary outcome is reduction in relapse, as rated from service user records using the definition of a "two-week exacerbation of symptoms leading to a change in management". Our secondary outcomes are Positive and Negative Syndrome Scale (PANSS), Personal and Social Performance Scale (PSP), Perceived Criticism Scale (PCS), Brief Illness Perception Questionnaire (Brief-IPQ), Knowledge About Psychosis Interview (KAPI), General Health Questionnaire (GHQ-12), generic health status measure (EQ-5D-5L), Working Alliance Inventory (WAI) and Service Engagement Scale (SES).

As CaFI was not established with Sub Saharan African people, neither its acceptability nor the feasibility of recruitment and retention has been tested in this population. We plan on testing CaFI with African families in an internal pilot, which will be embedded in the RCT. Depending on the outcome of the pilot, we will either continue with a Caribbean only sample at this stage or incorporate the African sample in to the main study.

Qualitative adaptation work

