Service use data will be collected from patient records (hospital inpatient, outpatient and accident & emergency services) and from a Service-Use Interview (SUI) with participants and family at baseline and at each follow up assessment. The SUI will include questions about whether the participant has used any primary, secondary or community-based health and social care and how often they used the service in the last 3 months (baseline study visit) or since the last assessment (follow-up study visits).

The SUI will ask participants to record whether they have used any hospital inpatient, outpatient or emergency services and the name of the hospital, to facilitate the review of patient records.

The SUI will also include time spent by family as informal carers, use of other public services (e.g. criminal justice system) and time in paid and unpaid employment/productive activity. These data will be used to estimate costs for a broader societal perspective for sensitivity analysis.

Timetable (months) and participant timeline

Total duration: 42 months

1-22 months: Recruiting people to test CaFI and making sure CaFI is acceptable to both Sub Saharan Africa and Caribbean descent

1-40 months:

- Recruiting more people to test CaFI and delivering CaFI to family units
- Collecting information before receiving CaFI
- Collecting information directly after receiving CaFI
- Collecting information 6 months after receiving CaFI
- Collecting information 12 months after receiving CaFI
- Analysing the collect information

31-42 months: share findings with the public (including service users and families), health professionals, policy makers and academics

Participant timeline

Participant recruitment: 22

Duration of intervention/participant: 10 weeks within 20-week therapy window

Duration of follow-up: 12

Trial duration/participant: 17 (including follow-up)

Table 1. Schedule of participant enrolment, interventions and assessments in the CaFI study.

	STUDY PERIOD					
	Enrolment	Allocation	Post-allocation			Close- out
TIMEPOINT**	-t1 Baseline	t ₁	t2 Post- interve ntion	t ₃ 6- month follow-up	t4 12-month	t _x

The University of Manchester			people v	vith psychos	es		NHS Found
ENROLMENT:							
Eligibility screen	X						
Informed consent	X						
Randomisation		X					
INTERVENTIONS:							
Culturally-adapted							
Family Intervention		+					
Treatment as Usual		-					
ASSESSMENTS:							
Relapse data (health records)	X			X	X	X	

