Based on our sample size calculation, we will need to recruit 16 participants per month across all seven NHS Trusts to reach target. Recruitment will be rigorously monitored throughout the recruitment period. 12 months from starting recruitment, we expect to have recruited 60-80% of our family units. As with most trials, we anticipate recruitment may be slow initially. If at 6 months we have recruited 60 families (10 per month), will consider options for boosting uptake. At the 9 months review, if we have recruited less than 60% of the 9 month target we shall consider opening one or both contingency sites. If we have achieved 80% or more of the 12 months target, we will continue without change. Similarly, if recruitment is less than 50% at the 12 months review, the trial may be stopped after discussion with the Trial Steering Committee, Data Monitoring and Ethics Committee (DMEC), and funders.

Data management: A web based electronic data capture (EDC) system will be designed, using the InferMed Macro 4 system. The EDC will be created in collaboration with the trial analyst/s and the CI and maintained by the King's Clinical Trials Unit for the duration of the project. It will be hosted on a dedicated server within KCL.

The CI or delegate will request usernames and passwords from the KCTU. Database access will be strictly restricted through user-specific passwords to the authorised research team members. It is a legal requirement that passwords to the EDC are not shared, and that only those authorised to access the system are allowed to do so. If new staff members join the study, a user-specific username and password must be requested via the CI or delegate (e.g. Trial Manager) from the KCTU team and a request for access to be revoked must be requested when staff members leave the project. Study site staff

experiencing issues with system access or functionality should contact the CI or delegate (e.g. Trial Manager) in the first instance.

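### The stated recruitment rates (16 and 17 per month) do not deliver 404 in 22 months, and the 12-month expectation and review thresholds are not tied to either rate

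*Protocol*

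**What the plan says.** All references are to the Phase 2 protocol unless stated.

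- **Target.** Sample size: "Inflating for the expected 2% drop out, we require a total sample size of 404". Design rationale: "We will recruit 404 family units (all sites combined) which equates to 202 family units in each arm".
- **Rate.** Sample size: "we will need to recruit 17 participants per month across all NHS Trusts". Interim analyses and stopping guidelines: "we will need to recruit 16 participants per month across all seven NHS Trusts to reach target". Both are presented as following from the same sample size calculation.
- **Period.** Timetable and participant timeline: "Participant recruitment: 22" (months). Each participant is in the trial for 17 months including follow-up. Recruitment, data collection and analysis are placed in months 1-40 of a 42-month study.
- **Expected progress.** Interim analyses and stopping guidelines: "12 months from starting recruitment, we expect to have recruited 60-80% of our family units". The section then says that recruitment may be slow at first.
- **Review rules, same section.** At 6 months: "If at 6 months we have recruited 60 families (10 per month), will consider options for boosting uptake". At 9 months, below 60% of that month's target, the contingency sites are considered. At 12 months, 80% or more of that month's target means no change. Then: "if recruitment is less than 50% at the 12 months review, the trial may be stopped", after discussion with the two oversight committees and the funders. No count is given for the 9- or 12-month target.

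**The concern.** Two different monthly rates are said to reach the same target, and neither appears to do so in the stated period. The expected position at 12 months looks far above what either rate would produce, although a slow start is anticipated. The 9- and 12-month rules are percentages of targets that are never stated, and the stopping criterion does not say what its 50% is a percentage of.

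These figures feed the Stop/Go internal pilot and the decision to open contingency sites. If they disagree, those judging progress cannot tell from the protocol whether the trial is on schedule. A trial that meets its stated rate would also finish recruitment short of 404.

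**Working it through.** **Inputs.** From the Phase 2 protocol: total 404; recruitment 22 months; 17 months per participant; data collection and analysis to month 40; rates 16 and 17 per month; 60-80% expected at 12 months; relapse 40% v 24%; ICC 0.01 in the intervention arm; cluster size 11; 2% loss; 90% power. Assumed: two-sided 5% significance, which the protocol does not state, and recruitment starting in month 1.

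**1. The target reproduces.** With mean risk 0.32, difference 0.16, z = 1.960 and 1.282:

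- n = [1.960√(2×0.32×0.68) + 1.282√(0.40×0.60 + 0.24×0.76)]² / 0.16² = 176.5
- With continuity correction: (176.5/4)[1 + √(1 + 4/(176.5×0.16))]² = 188.8, so 189 per arm.
- Design effect in one arm: 1 + (11−1)×0.01 = 1.10, average 1.05. 189×1.05 = 198.45, matching the stated 198.
- 2×198×1.02 = 403.9, so 404.

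**2. Rate needed:** 404/22 = 18.4 per month. In whole numbers this is 19 (19×22 = 418), since 18×22 = 396 falls short.

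**3. What the stated rates give**

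| Rate | In 22 months | Months to reach 404 | Last participant finishes (+17) | At month 12 |
|---|---|---|---|---|
| 16 | 352 (87%) | 25.25 | month 42.3 | 192 (47.5%) |
| 17 | 374 (93%) | 23.8 | month 40.8 | 204 (50.5%) |

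The timetable has little slack. 40 − 17 = 23 months at most for recruitment, and 17×23 = 391 is still short.

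**4. The 12-month expectation.** 0.60×404 = 242 and 0.80×404 = 323, or 20 to 27 per month from the start. Neither stated rate comes close.

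**5. The 12-month lines under each reading of the denominator**

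| 12-month target taken as | 80% line | 50% line | Position of 192 |
|---|---|---|---|
| 16×12 = 192 | 154 | 96 | on target |
| 17×12 = 204 | 163 | 102 | above both |
| 18.4×12 ≈ 220 | 176 | 110 | above both |
| 60-80% of 404 = 242-323 | 194-258 | 121-162 | above stop line, just below or below the 80% line |
| 50% taken of all 404 | – | 202 | below stop line |

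The stopping line therefore lies anywhere from 96 to 202.

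**6. Power if recruitment closes at 22 months.** On the continuity-corrected basis of step 1, effective n per arm = N×0.98/2/1.05:

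- 404: 188.5, about 90%.
- 374: 174.5, about 87%.
- 352: 164.3, about 85%.

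**The case against.** The strongest reply is that these are advisory feasibility markers. The sample size, allocation, outcome and analysis do not depend on them. Stopping is only possible after discussion with the Trial Steering Committee, the Data Monitoring and Ethics Committee and the funders, who would see whether recruitment was on pace. That stands, and it limits the severity.

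A reader might infer that the plan would stop a trial running exactly at 16 per month, because 192 is 47.5% of 404. The document does not support this as a firm claim. The stopping sentence is linked by its opening word to the sentence before it, which measures progress against the 12-month target. Half of that target is the more natural reading, and an on-pace trial then stands at 100% with a line at 96. Only division by the full 404 puts it below the line. What remains is an ambiguity: the denominator is missing, and the same paragraph also measures progress against all family units.

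A reader might also project that a trial allowed to carry on at 80% of a 192 target (154) would end near 282 with much lower power. That assumes the early pace never improves, whereas the plan expects a slow start and provides for boosting uptake and opening contingency sites.

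It can also be said that 17 per month is right for a longer period: 404/24 = 16.8, and the Phase 1 protocol allowed 24 months. That may be where the figure came from, but this is inference. The Phase 2 timetable says 22 months, and 16 per month fits neither period. Finally, the 6-month wording is plainly a drafting slip whose only consequence is that options are considered.

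**Conclusion.** The inconsistency is real and rests on the protocol's own figures. The two rates differ, and both fall short of 404 over 22 months, by 52 (at 16 per month) and 30 (at 17). At either rate, reaching 404 overruns month 40, assuming recruitment starts in month 1. The 60-80% expectation fits neither rate. The 9- and 12-month targets have no numbers and the 50% criterion has no denominator, so the 12-month review cannot be applied unambiguously. It is not established that an on-pace trial would be stopped.

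If recruitment simply closed at 352, power would be about 85% against the planned 90%, assuming a two-sided 5% test and the continuity-corrected method that reproduces 198 per arm. This should be fixed. It does not undermine the design.

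**What to change.** 1. Make the sample size, timetable and stopping sections agree on one rate and one period that deliver 404. If 22 months stands, the rate is 18.4 per month (19 in whole numbers). If a lower rate is preferred, lengthen the recruitment period and restate the timetable to match. That choice is the sponsor's.
2. State the cumulative targets as counts. At 18.4 per month these are about 110 at 6 months, 165 at 9 and 220 at 12.
3. Apply the plan's existing percentages to those counts and name the denominator each time: below 99 (60% of 165) at 9 months; at 12 months, 176 or more (80% of 220) to carry on and below 110 (50% of 220) to discuss stopping. A trial at exactly 176 would reach only about 323 by month 22 at constant pace (176/12×22), so the 80% line tolerates a shortfall that must be caught up later.
4. Word the 6-month trigger as 60 or fewer.
5. Correct the 60-80% expectation, or say what it is a percentage of.

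The cost is a protocol text amendment. The required rate becomes somewhat less favourable, or the timetable longer. No change to sample size, randomisation or analysis is needed.
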